5.5. Safety and Monitoring Plan

Careful evaluation to ascertain the toxicity and clinical response will be performed. The principal investigator will monitor the data and toxicities to identify trends quarterly. The principal investigator will be responsible for revising the protocol as needed to maintain safety. The NCI IRB will review submitted adverse events

monthly to also evaluate trends and will require a follow up plan from the principal investigator whenever a trend is identified.

The trial will be monitored at least annually by the NCI/CCR DSMB. Interim outcome results will not be revealed to the investigators of the trial; results will be presented to the investigators prior to final accrual to the trial only if the DSMB recommends early termination of the trial. Until 68 patients have been randomized, only toxicity and adverse events will be examined at each review. Once 68 patients have been randomized, interim evaluations to determine whether there is sufficient evidence to terminate accrual because of a better than expected improvement in overall survival, will be performed as detailed in Section 5.4. At the first such review of outcomes, a single evaluation for futility will also be performed.

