5.4. Statistical Section

The primary objective of the trial is to determine if there is a difference in overall survival among patients with limited gastric cancer metastases who are randomized to receive either systemic therapy alone or gastrectomy, metastasectomy and systemic therapy.

Based upon results in the literature, patients who would be eligible for this trial and who receive systemic therapy alone would be expected to have an estimated 12-month median overall survival from the date of randomization. The goal of this study will be to determine if the use of gastrectomy, metastasectomy and systemic therapy will result in an 8-month increase in overall survival, to a median of 20 months. Patients will be randomized between systemic therapy alone or gastrectomy, metastasectomy and systemic therapy and followed for overall survival. Kaplan-Meier curves and a two-tailed log-rank test will be the primary analysis methods. Assuming exponential overall survival curves, the hazard rate for the systemic therapy is 0.0578, or approximately a 5.8% probability of death each month when the median survival is 12 months. If we assume that the surgery plus systemic therapy arm has a median overall survival of 20 months, this corresponds to a hazard rate of 0.0347, and the resulting hazard ratio for the comparison of the two overall survival curves would be 1.67. To compare these curves and detect a difference with a 0.05 two-tailed log-rank test, a total of 68 evaluable subjects per arm (136 total) will need to be enrolled over a 6-year period and followed for an additional 2 years from the date of entry of the last patient, with 121 total deaths, in order to have 80% power to compare the curves.

Patients will be stratified for site of metastases (liver, peritoneal, or lung), disease-free survival and prior systemic therapy for gastric metastases.

Progression-free survival will also be evaluated using Kaplan-Meier curves, and a two-tailed log rank test, as a secondary endpoint. In addition, a prognostic factor evaluation using Cox proportional hazards modeling will take place after the study has concluded in order to identify if there are factors which can be identified that are associated with survival or progression free survival in patients randomized to treatments on this trial; this will also be interpreted as a secondary endpoint.

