The study will be monitored by the NCI/CCR Data Safety and Monitoring Board on an annual basis to evaluate the safety of the two arms. The SAEs (typically grade 3 toxicities, or greater) will be reported according to type of toxicity, and maximal grade noted per patient, for toxicities with at least a possible attribution to the therapy provided on that arm. Comparisons will be made between the two arms using Cochran-Armitage tests for trend, or other appropriate methods, to determine if there is increased toxicity associated with either arm.

In addition, at the first Data Safety and Monitoring Board (DSMB) meeting held following the point at which half of the required total subjects have been enrolled (68 total), a single evaluation for futility will be undertaken. Evaluations for better than expected efficacy will also be made annually, beginning after half the subjects have been enrolled.

The futility evaluation will be performed as follows: based on the full data available at the time, a conditional power analysis will be performed to determine if the trial is unlikely to find an effect at the 0.05 two-tailed significance level with continued accrual based on an overall survival endpoint. Median survivals of 12 and 20 months correspond to 12-month survivals of 50% and 66% respectively. Using these as the values under the alternative, and using the actual proportions alive at 12 months, based on the observed fractions and the expected sample sizes at 12 months, the conditional power of the trial will be determined assuming accrual of the remaining patients to achieve a total of 136 patients. If the conditional probability of finding a difference at the two-sided 0.05 level at the conclusion of the trial is less than 20%, then it will be reasonable to recommend that no further patients will be enrolled.

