The evaluation for better than expected efficacy will be performed as follows. Beginning at the first annual DSMB meeting after 68 patients have been randomized, annual interim evaluations will be performed to determine if there is sufficient evidence to terminate accrual because of a better than expected improvement in overall survival. An alpha spending function approach to monitoring will take place using an O'Brien-Fleming interim evaluation boundary ⁷⁹. It will be assumed that a total of 121 deaths would take place over a total of 8 years of accrual plus monitoring, and that monitoring would begin after approximately 40-45 deaths have been noted. The information fraction used to compute the interim boundary at each annual evaluation will be calculated as the number of patients who died /121.

Quality of life evaluations will be compared between the two study arms, with comparisons at multiple individual time points, as well as with respect to changes from baseline. Wilcoxon rank sum tests will likely be used. The evaluation will be considered secondary, and p-values resulting from the analysis will be presented without adjustment for multiple comparisons, but in the context of the number of tests evaluated.

It is expected that 24 patients per year can be accrued onto this trial, and thus accrual will be completed in approximately 6 years. Allowing for a very small number of inevaluable patients, the accrual ceiling will be set at 140 patients.

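### The single futility rule counts a likely significant result against surgery as a reason to continue, and the plan does not plainly say which survival rates it projects forward

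*Combined protocol and SAP*

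**What the plan says.** Two interim rules use overall survival, both in section 5.4 and summarised in section 5.5.

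- **Efficacy.** Annual looks start at the first annual DSMB meeting after 68 patients are randomised. They use an O'Brien-Fleming alpha-spending boundary with information fraction deaths/121. Their stated purpose is to see whether there is "sufficient evidence to terminate accrual because of a better than expected improvement in overall survival". The plan expects about 40 to 45 deaths when this monitoring begins.
- **Futility.** Section 5.5 adds: "At the first such review of outcomes, a single evaluation for futility will also be performed". The criterion in section 5.4 is "If the conditional probability of finding a difference at the two-sided 0.05 level at the conclusion of the trial is less than 20" per cent; it is then reasonable to recommend closing enrolment. The calculation cites 50% and 66% 12-month survival as the alternative, and also the proportions actually alive at 12 months. No direction is named.

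Before that point, section 5.5 says: "Until 68 patients have been randomized, only toxicity and adverse events will be examined at each review". The annual between-arm safety comparison in section 5.4 covers toxicities at least possibly attributed to treatment and sets no threshold. Expedited death reports to the IRB (section 7.4.1) leave out deaths from progressive disease.

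**The concern.** A futility rule should recommend stopping when the experimental arm is unlikely to be shown better. This criterion asks how likely any significant difference is, so a probable significant result against GYMS raises the figure and pushes it above the 20% threshold.

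How much this matters depends on what is assumed for patients not yet observed. Section 5.4 names both the design alternative and the observed 12-month proportions, and does not say plainly which governs the remaining patients. The two readings can give opposite recommendations on the same data.

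The experimental arm carries operative risk: section 6.2 lists perioperative death, and section 1.2 cites 3.7% in-hospital mortality in the liver-resection series. Section 3.1.2 also lets systemic therapy start up to 16 weeks after surgery (24 with thoracotomy). A survival deficit that arose through delayed or missed chemotherapy need not appear as attributable toxicity. Once the single futility look has passed, no written survival guideline covers it.

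**Working it through.** **Inputs from section 5.4.** The final test is to "detect a difference with a 0.05 two-tailed log-rank test" with 80% power; medians are 12 and 20 months; "the resulting hazard ratio for the comparison of the two overall survival curves would be 1.67"; 121 deaths; 68 per arm; 24 patients a year.

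**The plan's own figures.** Required deaths = 4(1.960 + 0.842)² / ln(20/12)² = 120.3, rounded up to 121. The drift at 121 deaths is ln(20/12) × √121 / 2 = 2.81, and power is Φ(2.81 − 1.96) = 80.2%. Twelve-month survival is 0.5^(12/12) = 50% and 0.5^(12/20) = 66%. All agree with the plan.

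**Log-rank scale.** Let t = d/121, Z = −ln(HR)√d/2 with HR = GYMS/SA, and B = Z√t. The drift θ is 2.81 under the design alternative and Z/√t under the current trend. Let m = B + θ(1 − t). Then:
- benefit tail = 1 − Φ[(1.96 − m)/√(1 − t)]
- harm tail = Φ[(−1.96 − m)/√(1 − t)]

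The plan's criterion is the sum of the two tails.

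Example: d = 43, HR = 2. Here t = 0.355, Z = −2.27, B = −1.355 and √(1 − t) = 0.803.
- Design alternative: m = −1.355 + 2.81 × 0.645 = 0.456. Benefit tail 3.1%, harm tail 0.1%, total 3%: stop.
- Current trend: m = −3.81. Harm tail 99%: continue.

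| Deaths | GYMS/SA HR | Design alternative | Current trend |
|---|---|---|---|
| 43 | 1.5 | 12% (stop) | 63% (continue) |
| 43 | 1.8 | 5% (stop) | 94% (continue) |
| 43 | 2.0 | 3% (stop) | 99% (continue) |
| 60 | 3.0 | 30% (continue) | over 99% (continue) |

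The 30% and all the current-trend figures are essentially all harm tail.

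**12-month scale, which section 5.4 describes.** I used exact binomial probabilities for a pooled two-sided 0.05 z-test with 68 per arm at the end. The number with 12-month data at the look is an assumption: 22, 28 or 34 per arm, for a look 0, 6 or 12 months after the 68th patient at 24 a year ((68 − 24)/2, (68 − 12)/2, 68/2). SA is set at 50% observed.

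| GYMS v SA alive at 12 months | Design alternative | Current trend |
|---|---|---|
| 14/28 v 14/28 | 12% (stop) | 1% (stop) |
| 7/28 v 14/28 | under 1% (stop) | 92% (continue) |
| 4/34 v 17/34 | 16% (stop) | over 99% (continue) |
| 3/34 v 17/34 | 23% (continue) | over 99% (continue) |

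Under the design alternative with 22 or 28 per arm, every GYMS result at or below 50% gives less than 20% (maxima 18.9% and 18.6%). Under the current trend, equal survival stops the trial while half the SA survival continues it.

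**Benefit tail only.** With GYMS no better than SA on this 12-month scale, the largest value is 18.9% (11/22 in each arm) under either assumption, so every harm case above meets the rule.

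**After the look.** Deaths remaining: 121 − 45 = 76 to 121 − 40 = 81.

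**Mirrored O'Brien-Fleming-type boundary.** Taking 0.025 per side, the one-sided alpha spent at a first look is 2[1 − Φ(2.241/√t)], and the HR needed is exp(2z/√d). At 43 deaths z = 3.58 and HR is about 3.0. At 60 deaths z = 2.98 and HR is about 2.2.

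**The case against.** A reader might infer that no interim rule acts on worse survival in the surgical arm. The documents do not support that. The more natural reading of section 5.4 is that observed patients contribute their 12-month results and the rest follow 50% and 66%; a pure current-trend calculation would leave those two values without a role. On that reading the futility rule does stop for clear harm at the one look where it applies, short of extremes. The 63% to 99% figures therefore cannot be presented as what the plan prescribes.

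The log-rank version also continues at HR 1.25 (23% at 43 deaths), but that is benefit-tail probability under a mild deficit and does not come from the two-sided wording.

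Oversight is wider than the formal rules. The DSMB reviews at least annually, receives the survival evaluations once 68 patients are randomised, and may recommend early termination; nothing limits that to efficacy. Deaths not due to progressive disease reach the IRB within 7 working days. The futility rule is advisory, so a board seeing a clear deficit need not continue because of it. A single futility look is also a legitimate choice.

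All of this stands, and it narrows the point. What remains is that the criterion as worded counts harm toward continuing, the assumption for remaining patients is not plainly stated, and no survival guideline for harm exists at any later look.

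**Conclusion.** The point holds as a defect of wording in a stated decision rule; it is a cheap improvement. Under the best-supported reading the error bites only for extreme harm at a later-timed look: 9% v 50% alive at 12 months with 34 per arm, or a hazard ratio of 3 at 60 deaths. Under the alternative reading, which the text does not clearly exclude, it reverses the recommendation for hazard ratios of 1.5 to 2.0 at 43 deaths. Under either reading the futility rule is used once, and what follows is a boundary described only for improvement.

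The figures assume proportional hazards and Brownian-motion conditional power on the log-rank scale. On the 12-month scale they assume 22 to 34 patients per arm with data and 50% SA survival. The 76 to 81 remaining deaths rest on the plan's expected 40 to 45 at the first look. The 121-death sample size is not in question.

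**What to change.** In section 5.4:

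1. Define conditional power as the probability of a significant final result in favour of GYMS, and state that remaining patients are assumed to follow the 50% and 66% alternative.
2. Report this one-directional figure to the DSMB at each later annual look as non-binding guidance.
3. State that the annual boundary is two-sided and can also be crossed in favour of SA. Treat this as a backstop only: it needs a hazard ratio of about 3 at 43 deaths, so it would miss 1.5, 1.8 and 2.0, which the conditional power check catches at that look.

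Repeat the wording in section 5.5. The cost is a few sentences and one line per DSMB report. The symmetric boundary uses no extra alpha because the final test is already two-tailed, and the sample size does not change. The downside is a small loss of power if the repeated check is acted on.

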5.6. Clinical Trial Monitoring Plan

Harris Orkand Information Services (HOIS) provides study auditing/monitoring services under contract with the Center for Cancer Research, NCI. The number of patient records monitored is based on actual accrual. Below is a tabular summary of monitoring evaluations:

Time of year	Evaluation	# of records monitored	%data verification
1st quarter (Jan.- March)	Compare CRFs to source documentation, verify subject registration with Drug Accountability Records	3-4 study patients	100%
2nd quarter (April – June)	Compare CRFs to source documentation, verify subject registration with Drug Accountability Records	3-4 study patients	100%
3rd quarter (July – Sept.)	Compare CRFs to source documentation, verify subject registration with Drug Accountability Records	3-4 study patients	100%
4th quarter (Oct. – Dec.)	Compare CRFs to source documentation, verify subject registration with Drug Accountability Records	3-4 study patients	100%

*Based on expected accrual, 25% of enrolled patients will be monitored.

6. Human Subject Protection:

6.1. Rational for Subject Selection

The investigational nature and objectives of this trial, the procedure and the treatments involved, the attendant risks and discomforts, potential benefits and potential alternative therapies will be carefully explained to the patient in the clinic setting and in the hospital prior to treatment and prior to obtaining a signed Informed Consent. This is particularly important for this study because of the relatively unique nature by which the treatment is given. That is to say, the patients must subject themselves to a major operative procedure with the attendant risks and complications associated with it in order to receive treatment without any assurance of benefit from the treatment.

6.2. Evaluation of Potential Benefits and Risks

The potential benefit to patients undergoing this therapy would be palliation in terms of preventing or delaying intra-abdominal tumor progression and metastases elsewhere which can be a devastating and painful source of symptoms and cause for demise. In addition, significant tumor response may extend progression free and overall survival. The risks for this protocol include the risks associated with any abdominal surgery. This includes postoperative bleeding, intra-abdominal infection, enterocutaneous fistulas, anesthetic mishap and perioperative death. In addition, the toxicities of chemotherapy place the patients under risk. A combination of surgery and chemotherapy may decrease healing at a time when healing of abdominal wounds and bowel anastomosis is essential for recovery. All attempts will be made to avoid enterotomies or a bowel resection where feasible. In the case of intraabdominal catastrophe after surgery, patients may require reoperation.

6.3. Risks/Benefit Analysis

Patients dying of peritoneal carcinomatosis suffer with recurrent bowel obstructions, nausea, vomiting, crampy abdominal pain and incapacitating ascites. This clinical scenario justifies aggressive treatment strategies as a means of palliation and survival benefit. In Phase I and II trials we have seen long-term remissions after CHPP in patients who were otherwise terminal with no other therapeutic options available.

The potential benefit is great for these patients if a regional response is obtained. Therefore, this protocol involves greater than minimal risk, but presents the prospect of direct benefit to individual subjects.

6.4. Consent Process

All patients are thoroughly screened prior to initial consultation at the NIH. This usually involves a telephone conversation between the patient and a physician or nurse associate investigator. During the initial consultation the patient, along with family members, is presented a forthright and detailed overview of the treatment option available to them at the NIH. The experimental nature of the treatment, its theoretical advantages and disadvantages, and an overview of the operative procedure and anticipated convalescence are presented. The fact that the patient may undergo an operative procedure in order to receive therapy without any assurance of benefit, the aggressive nature of the treatment, and the likelihood of serious or potentially life-threatening complications are presented. The Informed Consent document is given to the patient and they are asked to review it, make notes and follow-up with a phone call to the physician or nurse investigator to have any additional questions answered prior to considering treatment on protocol.

When the patient is admitted to the Clinical Center for treatment, an associate physician investigator responsible for the care of the patient presents the previously described information in detail. The research nurse or Principal Investigator, or designee is responsible for obtaining consent from the patient upon admission. The patient is reassured that participation on the trial is entirely voluntary and that they can withdraw or decide against treatment at any time without adverse consequences. In fact, the

investigators assure the patient that if alternate therapies are preferred that we will do all that we can to facilitate obtaining consultation and treatment from the appropriate medical center. The signed consent will be verified by the physician responsible for the care of the patient. The patient is asked to participate in completing the self-administered questionnaires measuring health related quality of life during this study. They are assured that their eligibility to participate in the perfusion portion of this study is not dependent upon their willingness to complete the quality of life questionnaires.

7. Data Reporting:

7.1. DEFINITIONS

7.1.1. Adverse Event

An adverse event is defined as any reaction, side effect, or untoward event that occurs during the course of the clinical trial associated with the use of a drug in humans, whether or not the event is considered related to the treatment or clinically significant. For this study, AEs will include events reported by the patient, as well as clinically significant abnormal findings on physical examination or laboratory evaluation. A new illness, symptom, sign or clinically significant laboratory abnormality or worsening of a pre-existing condition or abnormality is considered an AE. All AEs must be recorded on the AE case report form unless otherwise noted above in Section 6.1.

All AEs, including clinically significant abnormal findings on laboratory evaluations, regardless of severity, will be followed until satisfactory resolution. AEs should be reported up to 30 days following the last dose of study drug. AEs that are considered treatment related, expected, continuing, but not resolvable by 30 days after treatment completion (e.g., alopecia) will not be followed after the 30-day period.

7.1.2. Suspected adverse reaction

Suspected adverse reaction means any adverse event for which there is a reasonable possibility that the drug caused the adverse event. For the purposes of IND safety reporting, 'reasonable possibility' means there is evidence to suggest a causal relationship between the drug and the adverse event. A suspected adverse reaction implies a lesser degree of certainty about causality than adverse reaction, which means any adverse event caused by a drug.

7.1.3. Unexpected adverse reaction

An adverse event or suspected adverse reaction is considered "unexpected" if it is not listed in the investigator brochure or is not listed at the specificity or severity that has been observed; or, if an investigator brochure is not required or available, is not consistent with the risk information described in the general investigational plan or elsewhere in the current application. "Unexpected", also refers to adverse events or suspected adverse reactions that are mentioned in the investigator brochure as occurring with a class of drugs or as anticipated from the pharmacological properties of the drug, but are not specifically mentioned as occurring with the particular drug under investigation.

